5.2 Health facility survey

The validity of women's reports on RMC (objective 2) will be determined from studies within the health facility survey. IDEAS project conducts a bi-annual survey of MNH facilities in the State during the same time period as the household survey. In the intervention area all 57 priority facilities are surveyed. In comparison areas, a sample of 40 primary level facilities are surveyed, sampled by identifying the primary level facility assigned to provide routine MNH care to the sampled household cluster. In addition, the 17 referral facilities in the State are also surveyed to capture information on emergency care. At each facility an inventory of infrastructure, supplies and staff employed is recorded, in addition to data extraction from maternity registers on the volume of events taking place in each facility during the six months prior to survey, other components of the facility survey include a birth attendant survey (all facilities), and observation of births and exit interviews in the 10 highest volume facilities.

5.2.1 Observation of births

Sample – this is nested within the facility survey in a sub-set of the 10 highest volume primary facilities within the intervention area facility sample. Using data on volume of births in each of the 57 priority facilities, facilities were ranked from highest to lowest number of births in the six months prior to survey and the top ten selected. In each of these ten facilities, and alongside the facility survey, two medically trained observers are posted in shifts covering day and night deliveries, 7 days a week (for approximately 3 weeks, determined by volume of births and time taken to recruit a sample of 320 births (see IDEAS Gombe data collection protocol for further details)). During working shifts these observers identify and observe women during labour and childbirth using a checklist to

document indicators of clinical and respectful care provided by birth attendants. Data collectors will be well trained to maximise the reliability of assessment.

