1.2 Overview of this study

The IDEAS project is part of this wide partnership with GSPHCDA, Pact, SFH, C4C and E4A working on MNH in Gombe, as a measurement, learning and evaluation (MLE) grant. IDEAS project aims to improve the health and survival of mothers and babies through generating evidence to inform policy and practice. In line with IDEAS project's overarching aim, the study described here will generate empirical evidence on the quality of MNH care as it relates to the frequency and nature of RMC during institutional delivery in Gombe state, to inform state-level and global actions to better promote RMC, and to improve measurement methods for RMC. The study will aim to answer the following the research questions:

Q 1 What is the prevalence of respectful maternity care during institutional delivery in Gombe State? (Objective 1)

To be determined in two ways: 1) prevalence of respectful maternity care based on how frequently mothers regarded the interaction with health workers or health facility conditions

during their last institutional delivery to be respectful, through household surveys of mothers with births in the 24 months prior to interview; 2) prevalence of RMC based on how frequently the interactions with health workers or facility conditions during institutional delivery are deem (by general consensus) to be humiliating or undignified, through observation of births (in line with submission by Freedman et al¹¹).

Q 2 What is the validity of self-reported measures of respectful maternity care?

To be determined by comparing observable respectful maternity care behaviors documented during observation of births as gold standard measures of RMC, compared to reported occurrence of RMC during exit interview with observed women on discharge from facility and again during household-follow interview with observed women 6-12 months after birth to test the validity of self-reporting i.e. do women report their experience of RMC consistently, and extent of normalization of RMC i.e. the extent to which some aspect of RMC are normalized in Gombe.

Q 3 What utilities do women attach to dimensions of respectful maternity care during institutional delivery in Gombe State?

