5.2.4 Data analysis

Table 4: Analysis plan

Research questions	Data sources	Analysis
Objective 1 – To determine the prevalence of respectful care during institutional delivery in Gombe state	Household survey	 Descriptive statistics to profile the study sample in numbers & percentages Descriptive statistics to determine the frequency of reported cases of respectful care from household interviews Descriptive statistics to determine the frequency of reported case of respectful care across socio-demographics Appropriate regression models will be used to explore the relationship between respectful care indicators and demographic characteristics. Potential confounders will be accounted for in all regression models
Objective 2 – To validate self-report of respectful maternity care	Observation of birth (gold standard) Exit interviews Follow-up interviews	 Descriptive statistics to characterize the study sample in numbers & percentages Descriptive statistics to determine the frequency of observed cases of respectful care from direct observation of births, exit and follow-up interviews Descriptive statistics to determine the frequency of reported case of respectful care across socio-demographics

- Sensitivity and specificity
- McNemar's test

Table 5: Socio-demographic characteristics & potential cofounders

Potential confounders	Measures
Age in years	Mean/ SD
Education level	Primary or less/ Secondary or more
Religion	Christianity/ Islam/ Other/ None
Ethnic group	Fulfulde/ Hausa/ Igbo/ Yoruba/ Others
Marital status	Never married/ Married/ Divorced/Separated/ Widowed
Employment status	Employed/ Unemployed
Wealth quintile	Lowest/Second/ Middle/ Fourth/ Highest
Number of previous births	Mean/ SD
Antenatal care visits for the/ index pregnancy	Mean/ SD
Time of delivery	Day/ Night
Days of the week (for observation of births)	Monday/ Tuesday/ Wednesday/ Thursday/ Friday/ Saturday/ Sunday

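### Observed births in ten high-volume intervention-area facilities are named as a route to RMC prevalence in Gombe State, which they cannot estimate, and the definition runs opposite to the household measure

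*Protocol*

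**What the plan says.** **Target.** Protocol section 1.2 asks as Q1: "What is the prevalence of respectful maternity care during institutional delivery in Gombe State". Two routes follow. The first counts how often mothers regarded the interaction or conditions "during their last institutional delivery to be respectful, through household surveys of mothers with births in the 24 months prior to interview". The second, also labelled prevalence of RMC, counts how often interactions or conditions "are deem (by general consensus) to be humiliating or undignified, through observation of births". Section 4.2 (data collection phase) again lists observation of birth, with household surveys and exit interviews, as a source of RMC prevalence data, and says that later rounds will update RMC indicators in the results framework.

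**Observed sample.** Section 5.2 describes the wider facility survey: "In the intervention area all 57 priority facilities are surveyed", together with a sample of 40 comparison-area primary facilities. "In addition, the 17 referral facilities in the State are also surveyed". Section 5.2.1 restricts observation: "this is nested within the facility survey in a sub-set of the 10 highest volume primary facilities within the intervention area facility sample". On selection it says "facilities were ranked from highest to lowest number of births in the six months prior to survey and the top ten selected". The target is 320 births.

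**Analysis plan.** Section 5.1 bases population-level prevalence (Objective 1) on the household survey. Table 2 credits observation to Objectives 2, 4 and 5. Table 4 gives the household survey as the only data source for Objective 1 ("Descriptive statistics to determine the frequency of reported cases of respectful care from household interviews") and uses observation as the gold standard for Objective 2.

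**The concern.** Three things do not fit together.

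- **Population.** Q1 is about all institutional deliveries in the state. The observed births come from a purposive set of facilities in one half of it (57 of 114 wards, section 4.1), where the supply-side strategy includes improving RMC (section 1.1). No weighting or limit on inference is stated.
- **Direction.** Under one label, a higher figure means better care by the household route and worse care by the observation route.
- **Role.** Sections 1.2 and 4.2 give observation a part in Objective 1. Section 5.1 and Tables 2 and 4 do not.

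Section 7 sends results to implementation partners and into the Gombe results framework. If Q1 is followed as written, a figure from ten facilities could be reported there as state prevalence, beside a household figure that counts the opposite kind of event.

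**Working it through.** **1. The protocol's own prevalence figure.** Section 5.1 requires 593 interviews, from p = 0.5, precision ±5 points, 95% confidence, a cluster effect of 1.4 and 10% losses.

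n = 1.96² × 0.5 × 0.5 / 0.05² = 384.1, rounded up to 385; 385 × 1.4 × 1.10 = 592.9, so 593.

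The figure reproduces, but it belongs to the household survey. No precision basis is stated for the 320 observed births.

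**2. Coverage of the observation route** (sections 5.2 and 5.2.1).

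| Group surveyed | Facilities | Observed |
|---|---|---|
| Intervention-area priority | 57 | 10 (10/57 = 17.5%) |
| Comparison-area primary | 40 | 0 |
| Referral | 17 | 0 |

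These are counts of facilities, not births. The ten sites hold a larger share of births than of facilities, but the protocol does not give that share.

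**3. Sampling error is not the main problem.** The half-width is 1.96 × √(0.25 × DE / 320), where DE is the design effect.

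- DE = 1: 5.5 points
- DE = 1.4 (the household value): 6.5 points
- DE = 2 and 3 (assumed): 7.7 and 9.5 points

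More births would narrow these intervals but leave the selection as it is. Let w be the ten facilities' share of the state's facility births, and D their prevalence minus that in all other facilities. Then

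bias = p₁₀ − [w·p₁₀ + (1 − w)·p_other] = (1 − w)·D.

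The protocol gives neither w nor D. Purely as an illustration, if D is 10 points in either direction, the bias is 0.9 × 10 = 9 points at w = 0.1 and 0.5 × 10 = 5 points at w = 0.5, with the sign of D.

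**4. Polarity, side by side.**

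| Place | What is counted |
|---|---|
| Section 1.2, Q1 route 1 | care regarded as respectful |
| Section 1.2, Q1 route 2 | events deemed humiliating or undignified |
| Section 5.2.1 checklist | indicators of respectful care |
| Table 3 (observed births, March 2017) | respectful acts, e.g. companion allowed 58%, desired privacy 23% |
| Section 1.2, Q2 | observable respectful behaviours |

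Only route 2 of Q1 runs the other way.

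**5. Role of observation, side by side.** For Objective 1: sections 1.2 and 4.2. Not for Objective 1: section 5.1, Table 2 and Table 4. Section 5.2 also ties the facility studies to Objective 2.

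**The case against.** The strongest reply is that the operative sections are already right. Section 5.1 and Tables 2 and 4 produce no state estimate from observed births, and ten busy sites are a sensible, feasible choice for validating self-report, which is the role those tables give the sample. Both points stand. The ten-facility frame is not a fault for Objective 2. What the reply does not remove is that Q1 is the stated research question, that section 4.2 repeats its claim, and that nothing says which text governs.

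Some stronger readings are tempting, and the documents do not support them:

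- **That observation fails to measure respectful care.** The checklist and Table 3 measure it directly. The fault is the definition in Q1, not the instrument.
- **That sensitivity and specificity would be swapped in Objective 2.** Q2 and sections 5.2.2 and 5.2.3 speak throughout of respectful or RMC behaviours, observed and reported in the same women. The inverted phrase occurs only in Q1.
- **That a gap between household and observed figures would be taken as reporting error.** Validity is tested within the observed women; no such comparison is planned.
- **That the Table 3 values can simply be flipped to show the effect.** Absence of a respectful act is not the same as an event judged humiliating.
- **That the bias is upward.** The programme might raise respectful care, but the protocol has no data on how high volume affects it.

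**Conclusion.** The point holds as a mismatch between the Q1 claim and the sample, joined to an inverted definition and an internal contradiction about Objective 1. Observation covers 17.5% of the priority facilities, selected by volume, and none of the 40 comparison-area or 17 referral facilities surveyed. It can describe care in those ten facilities but cannot estimate RMC prevalence in Gombe State. Neither the size nor the direction of the bias can be determined from the protocol; the 5 to 9 points shown above rest on assumed values of w and D. The conclusion itself rests on the stated sampling frame and wording, not on those assumptions. It matters because it changes what the study may claim from observed births. It does not call for a new sample or cast doubt on Objective 2.

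**What to change.** 1. Reserve the term prevalence in Gombe State for the household survey.
2. Either remove observation from Objective 1, or report it as the observed frequency of respectful care among births in the ten highest-volume primary facilities of the intervention area.
3. If it is kept, define it with the same polarity as the household route and Table 3, and report mistreatment items separately under their own label.
4. Make sections 1.2, 4.2 and 5.1, Table 2 and Table 4 agree on whether observation contributes to Objective 1.

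**Cost.** Changes of wording and definition only, with no new data. The sponsor gives up a state-level claim from observed births. Objective 2 is unchanged.

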5.2.2 Exit interviews with observed women

Sample – each woman whose birth was observed (target recruitment of 320 women) is invited to interview as she leaves the facility. Women are asked a set of questions about the clinical and respectful care they received during labour and childbirth. Data collectors will be well trained to maximise reliability of assessment.

5.2.3 Household follow-up with observed women

Sample – each woman whose birth was observed and was interviewed after discharge before exit will be asked for her consent for a follow-up interview at home six months later. At follow-up, women will be asked the same set of questions and same choice experiment as in the exit interview. Data from the choice experiment at follow-up will be compared with data on choice experiment from the exit interview to assess the stability of derived utilities from time-1(t0-month) and time-2 (t6-months). Data collectors will be well trained to maximise reliability of assessment.

Sample size for validity testing of exit interview and household follow-up interview responses compared to the gold standard observations. To analyse the agreement between observed and reported RMC behaviours we will calculate sensitivity and specificity of reported to observed. This statistical approach does not test a specific hypothesis, but focuses on the width of the confidence intervals around agreement when interpreting results: the larger the number of follow-up interviews we are able to achieve the more narrow the confidence intervals will be.

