5.1 Household survey

Sample — prevalence of respectful maternity care at the population level (objective 1) will be determined through household survey data. IDEAS project conducts an annual household survey each year 2017-2018. The annual household survey use cluster sampling with 40 intervention household clusters and 40 comparison household clusters from 'priority' and 'non-priority' areas respectively, to generate population level coverage estimate of MNH indicators from women aged 13-49 years with livebirth 24 months prior to each survey. Each household cluster is defined as an enumeration area segmented to include 75 households. Enumeration areas are selected using simple random sampling from a list of all enumeration areas in each area. 3000 households are sampled in each area, a total of 6000 from the 80 clusters (40 intervention and 40 comparison clusters). From this sample, approximately 2000 women with recent birth are expected in total from the 6000 households, minimum of 100 women in each area (each 40 clusters). At each household, the household head is interviewed about residents and socio-economic characteristics, and each resident woman aged 13-49 is individually interviewed. Interviewed women with a live birth in the 12 months prior to survey are asked to complete a detailed survey module about their experiences during pregnancy through to post-partum periods for that birth.

Sample size - The previous household survey indicated coverage of institutional delivery to be 46%, thus the expected number of interviews with women who delivered in a facility in the last two years is approximately 1000. To estimate a proportion of 0.5 (most conservative) with high precision (to within +/- five percentage points) and with 95% confidence the required number of interviews with women who delivered in a facility is 593 (after adjusting for a cluster effect of 1.4 and 10% losses). The prevalence of an illustrative set of RMC indicators is shown in table 3. These indicators suggest that the conservative sample size estimate is appropriate across the range of indicators, while allowing the potential for further analysis as the project proceeds (for example to compare proportions over time, or to restrict births to those that occurred in the last 12 months rather than 2 years).

Table 3: Prevalence of illustrative RMC indicators based on observations of birth in 10 primary health facilities, March 2017

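### Objective 2 reads validity through confidence-interval width, but no allowance is stated for clustering of the 320 women in ten facilities, although the household survey has one

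*Protocol*

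**What the plan says.** Section 5.2 of the protocol places "observation of births and exit interviews in the 10 highest volume facilities". Section 5.2.1 explains the selection: "facilities were ranked from highest to lowest number of births in the six months prior to survey and the top ten selected". It also describes the observers: "In each of these ten facilities, and alongside the facility survey, two medically trained observers are posted in shifts". The target is in section 5.2.2: "each woman whose birth was observed (target recruitment of 320 women) is invited to interview as she leaves the facility". Follow-up at home is sought from the same women.

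The paragraph on sample size for validity testing in section 5.2.3 names sensitivity and specificity against direct observation and then says: "This statistical approach does not test a specific hypothesis, but focuses on the width of the confidence intervals around agreement when interpreting results". The only influence on width that it names is the number of women reached: "the larger the number of follow-up interviews we are able to achieve the more narrow the confidence intervals will be". It gives no expected half-width, design effect or retention figure.

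For Objective 2, Table 4 (section 5.2.4) lists descriptive statistics, "Sensitivity and specificity" and McNemar's test. It says nothing on how standard errors are to be computed.

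For Objective 1, section 5.1 reaches its required number of interviews "after adjusting for a cluster effect of 1.4 and 10% losses".

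**The concern.** Women in one facility share staff, routines and the observers who supply the reference standard. If an observer tends to over- or under-record an item, or if women in a facility tend to report an item in the same way, then errors in self-report are correlated within that facility. Simple binomial intervals for sensitivity and specificity, and the ordinary McNemar test, ignore this correlation.

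The omission falls on the quantity that section 5.2.3 makes the focus of interpretation. Intervals that are too narrow would make self-report items look more precisely validated than the data allow, and McNemar p-values would be too small. The protocol allows for clustering in a survey of 80 clusters but states no allowance for a sub-study of ten. The number of facilities is a design feature, and later analysis can reflect it but not undo it.

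**Working it through.** **The protocol's own figure.** Section 5.1 uses p = 0.5, a half-width of 5 points and 95% confidence.
- 1.96² × 0.25 / 0.05² = 384.2, rounded up to 385.
- 385 × 1.4 = 539, and 539 × 1.1 = 592.9, so 593.

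The stated 593 reproduces, so Objective 1 does allow for clustering. There is no corresponding figure for Objective 2 to reproduce.

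**Inputs for Objective 2**
- 320 women (section 5.2.2) in ten facilities (sections 5.2 and 5.2.1).
- Privacy item observed in 23% (Table 3): 320 × 0.23 = 73.6 observed positives, the sensitivity denominator, and 246.4 observed negatives, the specificity denominator. These are about 7.4 and 24.6 women per facility.
- Assumed: a true sensitivity and specificity of 0.70, so p(1−p) = 0.21; equal facility sizes; and an ICC of 0.01 to 0.20. The relevant ICC is that of reporting accuracy given what was observed. The documents give no value for it.

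**Formulas**
- Design effect: DEFF = 1 + (n/10 − 1) × ICC.
- Half-width: 1.96 × √(DEFF × 0.21 / n). With ten clusters, t on 9 df replaces 1.96 by 2.262.
- Approximate coverage of an unadjusted 95% interval: 2Φ(1.96/√DEFF) − 1.

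**Unadjusted half-widths**
- Specificity: 1.96 × √(0.21/246.4) = 5.7 points.
- Sensitivity: 1.96 × √(0.21/73.6) = 10.5 points.

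**With clustering**

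| ICC | Specificity DEFF | Half-width, z (t) | Unadjusted coverage | Sensitivity DEFF | Half-width, z (t) | Unadjusted coverage |
|---|---|---|---|---|---|---|
| 0.01 | 1.24 | 6.4 (7.3) | 92% | 1.06 | 10.8 (12.5) | 94% |
| 0.05 | 2.18 | 8.5 (9.8) | 81% | 1.32 | 12.0 (13.9) | 91% |
| 0.10 | 3.36 | 10.5 (12.1) | 71% | 1.64 | 13.4 (15.5) | 87% |
| 0.20 | 5.73 | 13.7 (15.8) | 59% | 2.27 | 15.8 (18.2) | 81% |

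**A less extreme item.** At 47% prevalence (Table 3) there are about 150 positives. With a sensitivity of 0.80, the half-width is 6.4 points unadjusted, against 6.8, 8.3, 9.9 and 12.5 at the same ICCs.

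**The protocol's own 1.4, if it were carried over.** Intervals widen by √1.4 = 1.18, and unadjusted coverage is about 90%. With all 32 women per facility, 1.4 corresponds to an ICC of 0.4/31 = 0.013.

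**Effect of more interviews.** The variance is 0.21 × [(1 − ICC)/n + ICC/10]. It falls as n rises, but only towards 0.21 × ICC/10. At ICC 0.10 the half-width tends to 1.96 × √(0.0021) = 9.0 points, or 10.4 with t.

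**McNemar's test.** This uses all 320 women (32 per facility) and the same assumed range, here for the ICC of the paired difference. DEFF = 1 + 31 × ICC = 1.31, 2.55 and 4.10 at ICC 0.01, 0.05 and 0.10. A nominal 5% test then has a type I error of about 9%, 22% and 33%.

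**The case against.** Several parts of the case on the other side stand.

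- **Independence is not stated.** The protocol names measures but no variance method, and facility-clustered intervals would fit every word of it. The Objective 1 row of Table 4 is equally silent on clustering, although section 5.1 budgets for it. A reader might infer that the plan treats the women as independent, but the text does not say so.
- **The size is unknown.** Shared privacy or companion practice shows that the occurrence of care is clustered. Sensitivity and specificity condition on what was observed, so the ICC that matters is that of reporting accuracy. At 0.01 the effect is small. A reader might conclude that the intervals will be far too narrow, but the documents supply no ICC to support that. The privacy item also has the lowest prevalence of the respectful-care items in Table 3, which gives the largest specificity design effect among them.
- **The sentence on more interviews is not false.** Width does fall with every added interview. The sentence only omits that the gain is limited by the ten facilities.
- **McNemar's test is not a contradiction.** The statement that no hypothesis is tested can be read as covering sensitivity and specificity only. Testing for over- or under-reporting is a legitimate validity question, and replacing the test outright would be a preference.
- **Width is not the only criterion.** Section 5.2.3 makes it a focus of interpretation, and Table 4 lists other analyses.

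It could also be said that the standard-error method belongs in a statistical analysis plan that is not shown. That does not dispose of the point. The protocol itself sets out the precision rationale for this sub-study, and that rationale leaves out the clustering it allows for elsewhere.

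**Conclusion.** The point holds as an unstated allowance, not as a proven error. Objective 2 draws all its women from ten facilities and is interpreted through interval width. Neither the rationale in section 5.2.3 nor Table 4 provides for facility clustering, whereas section 5.1 does so for the household survey. If the listed analyses are run in their ordinary form, uncertainty is understated for any positive ICC.

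For the 23% privacy item, the true specificity half-width would be about 1.1 times the unadjusted one at ICC 0.01, 1.5 times at 0.05 and 2.4 times at 0.20. For sensitivity the factors are 1.03, 1.15 and 1.5. These figures rest on an assumed true value of 0.70, equal facility sizes, full recruitment of 320 and an assumed ICC range. Clustering by itself leaves the point estimates as they are. The point is worth correcting before analysis, but it does not undermine the study.

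**What to change.** In Table 4, state that sensitivity, specificity and the paired difference (reported minus observed proportion) are reported with intervals clustered on facility. Use either cluster-robust standard errors with t on 9 df or a facility-level bootstrap. If McNemar's test is kept, use a cluster-adjusted version.

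In section 5.2.3, qualify the sentence on the number of interviews by adding that ten facilities set a floor on the width. Give the expected half-widths for 320 women in ten facilities over a range of ICCs, such as 0.01 to 0.20, and say that the ICC is assumed.

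This needs only wording and analysis code. No recruitment or data collection changes. The downside is that the stated intervals will be wider.
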